post-bariatric subjects enrolled in STAMPEDE trial: In forty subjects with residual type 2 diabetes (age 50yrs, HbA1c 8.2%, BMI 32 kg/m²) 32 months following gastric bypass and SG, 3 month use of generic phentermine (15mg) resulted in a decrease in HbA1c (8.4 ± 1.3 to 6.8 ± 0.8 , $P < 0.05$) and body weight by a median of 6.5kg. The use of basal insulin (0.3u/kg/day) resulted in less of a decrease in HbA1c (8.1 ± 1.4 to $7.3\% \pm 0.5$) and a median weight gain of 1.5kg.

Summary of Preliminary Data

These preliminary data from our institution demonstrate that relapse of diabetes control does occur with increasing time of follow up from gastric bypass procedure. Additionally, weight regain from nadir weight loss achieved after gastric bypass increases with time of follow up from surgery. Moreover, inadequate weight/fat loss and poor rise of adiponectin depict surgical non-remitters and these factors might be targeted with medical therapies to enhance greater weight/fat loss and increase adipose tissue health.

DESCRIPTION OF THE RESEARCH PROTOCOL

Experimental Plan: This is a prospective, randomized, double-blinded clinical trial for patients with recurrent type 2 diabetes post-gastric bypass surgery that will compare a 6 month course of canagliflozin monotherapy vs. placebo on clinical outcomes of type 2 diabetes. The rationale for including those subjects that initially remit but later redevelop as opposed to those that never achieve remission following metabolic surgery is based on several factors. Those that never achieve remission following metabolic surgery may not have had type 2 diabetes (but rather be autoimmune or MODY) prior to surgery or have the

ability to generate insulin from very poor residual β -cell function. Alternatively, those that initially remit have the potential to achieve durable remission in the future and may likely respond to adjunctive medical therapy. RYGB, AB, and SG operations comprise the majority of the bariatric practice and approximately 20-40% of those that initially remit may re-develop diabetes within a 5 year timeframe. Following consent and a screening visit to assess eligibility and clinical status (i.e. historical, physical and biochemical parameters including glycemic control and a pregnancy test in females), a baseline visit with diabetes educator will take place to provide standard diabetes education, nutrition and exercise prescription.

Sample Size Considerations

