The primary analysis will be performed using a modified intent to treat analysis which includes all patients receiving at least one dose of the drug they were assigned. A secondary, per-protocol analysis may also be performed using those demonstrating compliance to their assigned treatment throughout the study. All endpoints will be evaluated using a significance level of 0.05, and no correction for multiple testing is planned.

To evaluate changes in HbA1c and other continuous endpoints at 6 months, analysis of covariance models will be fit. In these models, change from baseline will be the outcome, group membership will be the predictor of interest, and baseline level of the outcome will be a covariate. If distributional assumptions of the model are not met, transformation of the outcome measure will be considered to improve model fit, as will the use of alternative rank-based approaches. Estimated changes and differences in the changes at 6 months between groups will be presented with 95% confidence intervals. Categorical factors will be presented using frequencies and percentages, and comparisons of these measures between groups will be performed using Pearson chi-square tests or Fisher exact tests, as appropriate. Continuous patient characteristics will be summarized using means and standard deviations or medians and quartiles, depending on their distribution.

Inclusion Criteria:

1. Post-AB, RYGB, and SG patients who underwent surgery >1 and <15 years ago, in the Cleveland surrounding area
2. 20-75 years of age

3. DM2 diagnosis (history, medication usage, biochemical criteria) prior to and after surgery; after surgery, defined by a single HbA1c of greater or equal to 6.5% at consent and screening.

4. Metformin patients must have an HbA1c greater than or equal to 6.5% but less than or equal to 11% at randomization; for diet controlled patients (i.e. not on any T2D medication), HbA1c must be greater than or equal to 6.5% at randomization.

5. Patient reporting of improvement in T2D status or objective improvements in T2D status at any time post-surgery.

6. eGFR \geq 60mL/min prior to randomization

7. Has the ability and willingness to provide informed consent.

8. Is able to understand the options and to comply with the requirements of each program.

9. Female subject agrees to have a serum pregnancy test at screening. A negative serum pregnancy test result is required prior to randomization.

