10. Female patients must agree to use a reliable method of contraception for 6 months

or

duration of intervention.

11. Excluding research-related insulin use, patients taking an anti-diabetic medication, except insulin, are eligible and must

agree to washout for 8 weeks prior to the randomization visit.

Exclusion Criteria:

1. Type 1 diabetes indicated by history of diabetic ketoacidosis and lack of remission in response to bariatric surgery.

2. Other post bariatric procedures (banding, duodenal switch, biliopancreatic diversion)
3. Non-research-related insulin use that is prescribed by the patient's primary care physician or endocrinologist
4. End organ diabetic complications (renal failure, cardiomyopathy, severe neuropathy/foot ulcers)
5. Documented severe or unstable depression/anxiety or eating disorder that would not enable patient to adhere to anti-diabetic treatment.
6. Clinical contraindications to use canagliflozin, i.e., history of bladder cancer, Child-Pugh class C.

In addition to a urine sample, a maximum of 60-cc of blood may be needed at each visit; 30-cc will be stored as a biorepository, for future purposes. The biorepository will be performed at randomization and at the 6 month visit. The research repository collection will be part of the protocol. The identity of the subject will be confidential as the samples will be deidentified. Specimens will be processed and stored in Preventive Research Laboratory at Cleveland Clinic. Access to these specimens will be limited to the designated PRL laboratory personnel and utilized at the discretion of the Principal Investigator.

Schedule of visits summarized:

Visit 1: Consent and Screening Visit: An assessment of clinical status for eligibility will be performed. Review of past medical history and medication usage will be reviewed. Venipuncture for HbA1c and a pregnancy test (females only). Labs for nutritional status

including B12 and 25 hydroxy vitamin D will be performed. Nutritional deficiencies will be addressed per current clinical guidelines for post-bariatric patients.

Visit 2: Baseline Visit: 45 minute visit with diabetes educator for diet/exercise prescription and glucose monitoring based on ADA clinical care guidelines.

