Visit 3: Randomization visit with research coordinator and PI: Review of eligibility. Labs will be drawn for HbA1c, fasting glucose, lipid panel, uric acid, complete metabolic panel and adipokines (C-reactive protein, leptin, total and HMW adiponectin, leptin). Urine for albumin/creatinine ratio. DXA scan will be performed for body composition at this visit. Blood and urine will be collected for the bio-repository collection and is optional.

Visit 4: 6 week f/u visit: Research fellow/coordinator to assess adherence and safety.

Visit 5: 3 month visit with research coordinator and PI: Review of clinical status and biochemical labs will be drawn. These will include HbA1c and a complete metabolic panel.

Visit 6: 6 month visit with research coordinator and PI: Review of clinical status and biochemical labs will be drawn. These include HbA1c, fasting glucose, lipid panel, uric acid, complete metabolic panel and uric acid. Urine for albumin/creatinine ratio. Additionally, a DXA scan for body composition and blood for adipokines (C-reactive protein, total and HMW adiponectin, leptin) will be performed. Blood and urine will be collected for the bio-repository collection and is optional.

The window for all visits will be +/- 4 weeks.

Research Team: [name] is the principal investigator of this study and will consult with [name] (bariatric surgeon) for enrollment of appropriate candidates who underwent metabolic surgery at any Cleveland Clinic location, but that live within two hours of the Cleveland Clinic Main Campus. Both investigators have a long standing,

productive relationship. Statistical analysis will be provided by a Cleveland Clinic Quantitative Health Sciences statistician dedicated to endocrine and diabetes research. This team is well qualified to run post-bariatric trials and have successfully run two randomized control trial of bariatric vs. medical therapy for type 2 diabetes in obese patients.

POSSIBLE RISKS

Risks associated with Canagliflozin Include:

All drugs can cause unwanted effects called side effects. As of 28 September 2015 approximately 13173 subjects have received canagliflozin in completed or ongoing studies of 12 weeks or longer.

Side effects found in these studies that are more likely to occur with canagliflozin include those below. You should speak with your doctor about any changes to your diet or other medications you are taking:

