- **Amputation** of the toes (and to a lesser extent the foot or leg) could occur in up to 1 in 150 people per year on canagliflozin. This risk is greater in those with a prior history of amputation, disease of the circulation involving the legs or in those with nerve damage due to diabetes.
- **Decreased bone mineral density** - A clinical trial showed that canagliflozin caused greater loss of bone mineral density at the hip and lower spine than placebo.

Side effects in patients not involved in clinical studies who have been prescribed canagliflozin to treat their diabetes include those below. It is difficult to know specifically how often these side effects occur or always be certain if they are more likely to occur as a result of canagliflozin because these were not reported in the manner similar to data collection in a clinical study.

- Serious allergic reactions, including those with the symptoms of swelling of the face, throat, and/or tongue or breathing problems.
- Related to changes in lab tests associated with kidney function, severe cases of decreases in kidney function have been reported more commonly in patients who were dehydrated. Only subjects with an eGFR \geq 60mL/min will be enrolled into this study. While participating in this study, if a subject's lab results indicate a decline in eGFR between 45-60mL/min, the daily dose of canagliflozin will not exceed 100mg. If a subject's lab results indicate a decline in eGFR to <45mL/min, study medication will be withdrawn.
- Infections of the urinary tract that can spread to the kidneys or into the bloodstream.

Canagliflozin has been tested for its ability to cause harm to the fetus during pregnancy or cause birth defects. These studies have been done in animals. The studies that have been completed do not indicate that canagliflozin is associated with birth defects.

Nonetheless, women who are pregnant, lactating or intend to become pregnant during the study will be not allowed to participate in the study. Women who could possibly become pregnant

must have a negative pregnancy test prior to starting on the study drug and report immediately to the study site if they suspect they are pregnant during the study.

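### The only scheduled pregnancy test is at Visit 1 and its result has no maximum age, so an unrecognised pregnancy begun before randomization could be exposed to study drug

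*Combined protocol and SAP*

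**What the plan says.** **The requirement.** Inclusion Criteria, item 9: "Female subject agrees to have a serum pregnancy test at screening. A negative serum pregnancy test result is required prior to randomization". Possible Risks bars pregnant women from the study and says that a woman who could become pregnant "must have a negative pregnancy test prior to starting on the study drug". Neither place says how recent the result must be.

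**The schedule.** The Experimental Plan lists, among the screening assessments, "glycemic control and a pregnancy test in females". Under Schedule of visits summarized, Visit 1 has "Venipuncture for HbA1c and a pregnancy test (females only"). Visit 3 is described as "Randomization visit with research coordinator and PI: Review of eligibility", followed by "Labs will be drawn for HbA1c, fasting glucose, lipid panel, uric acid, complete metabolic panel and adipokines", a urine albumin/creatinine ratio and a DXA scan. No pregnancy test appears there, in the list of randomization assessments under Sample Size Considerations, or at Visits 2, 4, 5 or 6.

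**The interval.** Under item 11, patients on an anti-diabetic medication other than insulin must "agree to washout for 8 weeks prior to the randomization visit".

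**Contraception.** Item 10: "Female patients must agree to use a reliable method of contraception for 6 months" or for the length of the intervention. Possible Risks requires contraception throughout the study, with the method approved by the study doctor before entry.

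**The concern.** The protocol wants assurance that a woman is not pregnant when she starts study drug. A test answers that question for the day it is drawn. When an 8-week washout lies between the test and randomization, a negative result says nothing about conception during those weeks, yet it still satisfies item 9 as worded.

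Three things are at stake. The first is study-drug exposure in an unrecognised pregnancy, which Possible Risks sets out to prevent. The second is the loss of a randomized patient, because Adverse event reporting (section VI) requires prompt withdrawal and a report within 24 hours. The third is the blind for that patient: section VII has the Sponsor Investigator, who is also the principal investigator, submit an unblinded pregnancy-exposure report. A pregnancy found before randomization would avoid all three.

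**Working it through.** The plan gives no figure to reproduce here. The check compares the requirement with the schedule.

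1. **Number and place of tests.** The Experimental Plan, item 9 and the Visit 1 entry all put the test at screening. The two separate lists of randomization procedures (Sample Size Considerations and Visit 3) both omit it. Scheduled tests: one, at Visit 1.

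2. **Maximum age of the result.** Item 9 requires a negative result before randomization, and Possible Risks requires one before study drug. Neither sets a limit, so a negative Visit 1 result meets both on their wording, however old it is.

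3. **Age of the result at randomization.**
   - Women on a non-insulin anti-diabetic drug: age of result = (time from Visit 1 to start of washout) + 8 weeks. If the washout starts at or after Visit 1, the first term is zero or more, so the age is 8 weeks or more. That start is an assumption. Item 11 asks patients to agree to the washout, which implies it follows consent, but no start date is given.
   - Diet-controlled women: no washout and no stated interval between Visits 1 and 3, so no age can be calculated.

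4. **Whether another step closes the gap.** Eligibility is reviewed at Visit 3, and the text before Statistical Methods says the criteria are evaluated at both the screening and baseline visits. Neither review has a pregnancy test attached. HbA1c is a useful contrast: item 4 sets an HbA1c requirement at randomization, and the Visit 3 list redraws HbA1c. For pregnancy there is a requirement before randomization but no matching draw. Detection then depends on the woman suspecting a pregnancy and reporting it, as Possible Risks asks.

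5. **Contraception.** Item 10 covers 6 months or the intervention and does not name the washout. Possible Risks covers the whole study. The two differ on whether the weeks before randomization are included.

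6. **Likely frequency (illustration only).** The documents do not say how many women who could become pregnant will wash out. Assume 5 to 10 such women and an annual contraceptive failure rate of 1% to 10%. Expected conceptions over 8 weeks = women × annual rate × 8/52:
   - low: 5 × 0.01 × 8/52 = 0.008
   - high: 10 × 0.10 × 8/52 = 0.15

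   The event is unlikely in a trial of 36, but not negligible at the upper end.

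**The case against.** The strongest reply is that the protocol does not permit a pregnant woman to be dosed. Possible Risks bars pregnancy whatever item 9 shows, eligibility is reviewed at Visit 3, and contraception is required with a method approved before entry. This stands for a known pregnancy. A reader might infer from the schedule that any woman who conceives during washout would be enrolled and treated. The documents do not support that; they leave open only the unrecognised case.

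Second, item 9's second sentence can be read as calling for a fresh result near randomization. That is a fair reading, but on it the schedule omits a test that eligibility requires, so the text still needs correcting.

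Third, the schedule is headed as a summary and names neither body weight nor blood pressure at any visit, though both are secondary measures, so omission may mean little. This has some force. But the lists do name individual laboratory tests, they name the pregnancy test at Visit 1, and both randomization lists leave it out.

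Fourth, the stakes are modest. Eligible ages run from 20 to 75, the washout applies to only some women, and Possible Risks reports that completed animal studies do not link the drug to birth defects. One lost patient fits within the planned dropout allowance (24 − 22 = 2 on canagliflozin, 12 − 11 = 1 on placebo), although on placebo it uses the whole margin. All of this stands, and it limits the severity.

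**Conclusion.** The gap is real but narrow. The schedule has one pregnancy test, at Visit 1, and no text limits the age of its result. For women who wash out, the result would be about 8 weeks old or more at randomization, provided the washout starts at or after Visit 1. For diet-controlled women the age is unknown. An unrecognised pregnancy begun in that interval could be missed and exposed to study drug.

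Two tempting figures should not be used. Adding the 4-week visit window to the washout to obtain 12 weeks fails because Visit 3 has no nominal date, so 12 weeks is neither derived nor an upper bound. The 2 weeks of stable supplement doses do not set a minimum wait either, since a woman already on stable doses at Visit 1 need not wait. Nor do the documents show that contraception is absent during washout; they show two passages that disagree in scope.

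This is an inexpensive safety improvement. It does not affect the primary estimate.

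**What to change.** Add a serum pregnancy test to the Visit 3 blood draw, with the negative result known before randomization. State in item 9 and in Possible Risks that this is the result they refer to, and enter it in the Visit 3 list and in the randomization assessments under Sample Size Considerations. Keep the Visit 1 test. If a urine test is used at Visit 3 instead, item 9's requirement for a serum test must be changed to match.

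Reconcile the contraception period in item 10 with the one in Possible Risks. Which period is right is for the investigators to decide.

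The cost is one inexpensive test per woman who could become pregnant, a possible short wait for the result, and a few lines of protocol text. Blood is already drawn at Visit 3, so no visit or staff are added.
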